APPENDIX 08 – e-Delivery

Confidential

PIP-SICKLE

Page 1

Delivery

Record ID

Pregnancy Outcome	Miscarriage
	Pre-term Delivery
	 Term Delivery

Date of Miscarriage / Delivery

Gestation Age at Miscarriage / Delivery

(weeks)

(days)

BABY'S CONDITION AT BIRTH

Foetal Outcome	Alive
	Still Born
	Early Neonatal Death - Within 7 days of birth
	NNU Admission after 24 hrs Initial Observation
	Congenital Abnormality

Indication for Admission / Diagnosis

Congenital Abnormality

(Describe or Diagnosis)

Baby's Birth Weight

(g)

Head Circumference

(cm - 2 decimal places)

Baby's Length

(cm - 2 decimal places)

Confidential

Page 2

Apgar Score

(at 1 minute)

(at 5 minutes)

(at 10 minutes)

MATERNAL CONDITION AT MISCARRIAGE / DELIVERY

Maternal Complications

Pre-Eclampsia

Eclampsia

Sepsis

Pneumonia

Sickle Cell Crisis

Maternal Death

Others

Others

(Specify)

Sickle Cell Crisis

Vaso-occlusive

Haemolytic

Sequestration

Acute Chest Syndrome (ACS)

Severe Anaemia

Others

Others

(Specify)

Estimated Blood Loss

< 500 ml

500 - 1000 ml

> 1000 ml

Mother Physical Examination Within 1 Hour of Delivery

Maternal Weight

(kg - 2 Decimal Places)

Confidential

Page 3

BP

(Systolic)

(Diastolic)

Pulse Rate

Pulse Oximetry (SpO2)

Respiratory Rate

Temperature

LABORATORY

Haemoglobin Level

(At Today Visit)

Urinalysis Today

Leukocyte

- ± + ++

+++

Nitrite

- ± +

Urobilinogen

Negative Positive

Protein

- ± + ++

+++ +++++

Random Urine Sample Sent for UPCR

Yes No

pH

Blood		Negative	Positive
			
Specific Gravity			
Ketones		Negative	Positive
			
Bilirubin		Negative	Positive
			

08-06-2020 2:58pm

Powered by REDCap

Confidential

Page 4

Full Blood Count

Sample Taken for FBC

 Yes No

PCV

_____ (%)

Haemoglobin

_____ (g/dl)

Total WBC

_____ (cells/ml)

Neutrophils

_____ (%)

Lymphocytes

_____ (%)

Basophils

_____ (%)

Eosinophils

Monocytes

(%)

Platelet Count

(cells/ml)

Full Blood Count Result

Name of Clinician

CONFIDENTIAL

CONFIDENTIAL

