3.9 Outcome measures

Primary outcomes:

- Birth weight below 10th centile for gestational age on the WHO INTERGROWTH- 21st birthweight charts
- Stillbirth
- Fetal death
- Miscarriage.

Secondary outcomes:

Pregnancy complications: Pre-eclampsia, Preterm delivery, retained placenta, placental abruption;

Maternal complications: Maternal death, frequency of crises, no of blood transfusions, incidence of urinary tract infection, respiratory tract infection, acute chest syndrome, and potential adverse effects such as vaginal bleeding, epigastric pain and heartburn.

Preeclampsia will be diagnosed based on ISSHP classification (17) if there is development of hypertension (either systolic blood pressure ≥ 140 mm Hg or diastolic blood pressure ≥ 90 mm Hg on two occasions at least 4 h apart) after 20 weeks gestation plus one of the following: proteinuria, thrombocytopenia or any multisystem complication.

Proteinuria will be defined as a dipstick test with $\geq 1+$ proteinuria ($\geq 30 \text{ mg dl}^{-1}$) on two occasions at least 4 hours apart, without any evidence of a urinary tract infection. Or UPCR $>300 \text{ mg/g Cr}$.

Thrombocytopenia will be defined as platelet count $< 100,000/\text{Ul}$.

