5.5 Study Completion visit (Pregnancy loss or delivery)

A participant will be considered to have completed the study once there is a pregnancy loss or delivery at any time after randomisation and all relevant data is captured into the appropriate study completion CRF.

The following steps will be taken at the end of study visit

- ❖ Physical examination
- ❖ Evaluate compliance & ADE
- ❖ Complete all relevant documents
- ❖ Complete delivery e-CRF (*at delivery- Appendix viii*) and end of study visit e-CRF at completion of all study visits and data entry (*Appendix ix*) and other relevant source documents.

- ❖ Counselling and necessary referral (e.g Postpartum and family planning clinics)

Tables below lists all of the assessments and indicates with an “X” the visits when they are performed. All data obtained from these assessments must be supported in the patient’s source documentation. The Table indicates which data are entered into the database (D) or remain in source documents only (S) or both (SD).

Assessments that generate data for database entry and which are recorded on CRFs are listed using the CRF name (Enrollment, Visit, Study completion). Assessments that are transferred to the database electronically (e.g. laboratory data) are listed by test name.

Table 1: Study Visit Schedule

	Pre-treatment	Treatment (Enrollment and follow-up)																			Delivery			
Study Visit	0	1	2	3	4	5	6	7	8	9	10	11	12	13	14	15	16	17	18	19	20	21		
GA in weeks	6-11	12	14	16	18	20	22	24	26	28	29	30	31	32	33	34	35	36	37	38	39	40		
Screening	X	X	X	X	X	X	X	X	X															
Enrollment		X	X	X	X	X	X	X	X	X														
Follow-up			X	X	X	X	X	X	X	X	X	X	X	X	X	X	X	X	X	X	X	X	X	
End of study				X	X	X	X	X	X	X	X	X	X	X	X	X	X	X	X	X	X	X	X	

Table 2: Assessment schedule for study participants

Phase	Pre-Treatment	Treatment (Enrollment and follow-up)																	Delivery			
Study visit	0	1	2	3	4	5	6	7	8	9	10	11	12	13	14	15	16	17	18	19	20	21
GA in weeks	6-11	12	14	16	18	20	22	24	26	28	29	30	31	32	33	34	35	36	37	38	39	40
Inclusion/exclusion criteria (S)	X	X	X	X	X	X	X	X	X													
Written informed consent (S)	X	X	X	X	X	X	X	X	X													
Demographics/ PMH (SD)	X	X	X	X	X	X	X	X	X													
Concomitant medication (SD)	X	X	X	X	X	X	X	X	X	X	X	X	X	X	X	X	X	X	X	X	X	X
Body weight (SD)	X	X	X	X	X	X	X	X	X	X	X	X	X	X	X	X	X	X	X	X	X	X
Physical examination (SD)	X	X	X	X	X	X	X	X	X	X	X	X	X	X	X	X	X	X	X	X	X	X
Laboratory (SD) Hb +Urinalysis	X	X	X	X	X	X	X	X	X	X	X	X	X	X	X	X	X	X	X	X	X	X

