8.0 ADVERSE EVENTS AND REPORTING REQUIREMENTS

8.1 Adverse Events (AEs)

- ❖ An adverse event is the appearance or worsening of any undesirable sign, symptom, or medical condition occurring after starting the study drug even if the event is not considered to be related to study drug. Study drugs include the investigational drug/placebo under evaluation that is given during the treatment phase of the study.
- ❖ *Medical conditions/diseases present before starting study drug are only considered adverse events if they worsen after starting study drug.*
- ❖ Abnormal laboratory values or test results constitute adverse events only if they induce clinical signs or symptoms, or are considered clinically significant, or require therapy.

Clinical signs and symptoms will be assessed at baseline, before dosing and all follow-up visits, and recorded on the CRF. Any symptom that worsens or starts after baseline will be recorded as a new adverse event on the e-CRF.

The occurrence of adverse events, such as weakness, chills/rigors, headache, myalgia, dizziness, epigastric pain, abdominal pain, anorexia, nausea, vomiting, diarrhea, palpitations, insomnia, pruritus, coughing, tinnitus, abnormal gait, tremor, clonus or dyskinesia, will be sought by the investigator (or designee) at each study visit and recorded in the e-CRF.

Adverse events also may be detected when they are volunteered by the patient during or between visits or through physical examination, laboratory test, or other assessments.

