APPENDIX 07 e-follow up visit*Confidential*

PIPSICKLE

Visit

Page 1

Record ID

Date of Follow-up Visit

Gestational Age at FollowUp Visit

(weeks)

(days)

FollowUp Visit Type	Scheduled	Unscheduled
---------------------	-----------	-------------

Reason for Unscheduled Follow-Up Visit	Sickle Cell Crisis
	Pregnancy Complications
	Adverse Event Report

Others

Sickle Cell Crisis

Vaso-occlusive

 Haemolytic
 Sequestration
 Acute Chest Syndrome (ACS)
 Anaemia/Haemolytic
 Others
(Specify)

Others

Pregnancy Complications

(Specify)

Other Reason for Unscheduled Followup

(please specify)

Confidential

Page 2

ADVERSE EVENTS REPORT

Is there an Adverse Event (AE)? Yes No

Adverse Event (AE) - 1

(Brief description of the nature of AE)

Start Date

(dd-mm-yyyy)

Stop Date

(dd-mm-yyyy)

Severity Mild Moderate Severe (SAE)

Category of AE	Life Threatening
	Hospitalization
	Congenital anomaly
	Required intervention to prevent permanent impairment
	Persistent Disability / Incapacity
	Other

Other (Category of AE)

Relationship of AE to Study Drug	Unrelated
	Possibly Related
	Probably Related

Definitely Related

Action Taken No action taken (i.e. further observation only) Study drug dosage adjusted/temporarily interrupted Study drug permanently discontinued due to this adverse event Concomitant medication given Non-drug therapy given Patient hospitalized/patient's hospitalization prolonged

Add Another Adverse Event (AE)? Yes No

Adverse Event (AE) - 2

(Brief description of the nature of AE)

Start Date

(dd-mm-yyyy)

Stop Date

(dd-mm-yyyy)

Confidential

Page 3

Severity	Mild	Moderate	Severe (SAE)
Category of AE	Life Threatening		
	Hospitalization		
	Congenital anomaly		
	Required intervention to prevent permanent impairment		
	Persistent Disability / Incapacity		
	Other		
Other (Category of AE)			
Relationship of AE to Study	Unrelated		
	Possibly Related		
	Probably Related		
	Definitely Related		
Action Taken	No action taken (i.e. further observation only)		
	Study drug dosage adjusted/temporarily interrupted		
	Study drug permanently discontinued due to this adverse event		
	Concomitant medication given		
	Non-drug therapy given		
	Patient hospitalized/patient's hospitalization prolonged		
Add Another Adverse Event (AE)?	Yes	No	
Adverse Event (AE) - 3			
	(Brief description of the nature of AE)		

Start Date

(dd-mm-yyyy)

Stop Date

(dd-mm-yyyy)

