Severity	 Mild	 Moderate	 Severe (SAE)
----------	-------------------------------	-----------------------------------	---------------------------------------

Category of AE	 Life Threatening
	 Hospitalization
	 Congenital anomaly
	 Required intervention to prevent permanent
	 impairment
	 Persistent Disability / Incapacity
	 Other
	
	

Other (Category of AE)

Relationship of AE to Study Drug	 Unrelated
----------------------------------	------------------------------------

 Possibly Related
 Probably Related
 Definitely Related

Confidential

Page 4

Action Taken	No action taken (i.e. further observation only)
	Study drug dosage adjusted/temporarily interrupted
	Study drug permanently discontinued due to this adverse event
	Concomitant medication given
	Non-drug therapy given
	Patient hospitalized/patient's hospitalization prolonged

Any Admission since last visit?	Yes	No
---------------------------------	-----	----

if yes: Specify reason

Duration

Day(s) Week(s)

Month(s)

Have you had blood transfusion since last visit? Yes No

Date of blood transfusion?

How many units of blood?

Are you on any of the following drugs?

None

Paludrine

Hydroxyurea

Folic Acid

Penicillin V

-
-
- Multivitamin
-
- Ciklavit
-
- Astymin
-
- Jobelyn
-
- Vitamin B
-
- Vitamin C
-
- Others
-

Others

PHYSICAL EXAMINATIONS

Weight

(kg - 2 Decimal Places)

Weight

(g)

Fundal Height

(corresponding to week size)

Confidential

Page 5

BP

(Systolic)

(Diastolic)

Pulse Rate

Pulse Oximetry (SpO2)

Respiratory Rate

Temperature

LABORATORY

Haemoglobin Level (At Today Visit)

(g)

Urinalysis Today

Leukocyte

- ± + ++

+++

Nitrite

- ± +

Urobilinogen

Negative Positive

Protein

- ± + ++

+++ +++++

Random Urine Sample Sent for UPCR

Yes No

pH

Blood		Negative	Positive
			
Specific Gravity			
Ketones		Negative	Positive
			
Bilirubin		Negative	Positive
			

17-06-2020 7:50am

Powered by REDCap

Confidential

Page 6

Glucose

 - ± + ++ +++ +++++**Full Blood Count**

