2.2 Endpoints

Primary

1. IUGR, perinatal death or miscarriage as a composite outcome

The occurrence of either IUGR, perinatal death or miscarriage will be the primary outcome.

IUGR will be defined as birthweight <10th centile for gestational age on the INTERGROWTH-21st birthweight charts, which is based on a healthy reference cohort from multiple countries, including Kenya(16). IUGR based on the Oken charts from a US national reference(17) maybe presented in sensitivity. A perinatal death refers to the death of a fetus after the age of viability (≥ 28 weeks' EGA), at delivery, or within the first week of life. A miscarriage refers to pregnancy, loss the death of a fetus before the age of viability (< 28 weeks' EGA). All participants will do an ultrasound scan at 20 weeks to estimate the gestational age of the pregnancy. Analysis will be by intention to treat.

Hypothesis:

1. We expect a 50% lower incidence of IUGR, perinatal death or miscarriage in the LDA (intervention) group compared to the placebo (control) group.

Secondary

1. The incidence of preeclampsia. Preeclampsia will be diagnosed based on ISSHP classification(18) if there is development of hypertension (either systolic blood pressure ≥ 140 mm Hg or diastolic blood pressure ≥ 90 mm Hg on two occasions at least 4 h apart) after 20 weeks gestation plus one of the following: proteinuria, thrombocytopenia, or any multisystem complication. Proteinuria will be defined as a dipstick test with 1+ proteinuria (≥ 30 mg dl $^{-1}$) on two occasions at least 4 hours apart, without any evidence of a urinary tract infection, or 2+ proteinuria or more on dipstick, or urinary protein creatinine ration >300 mg/g. Thrombocytopenia will be defined as a platelet count of $<100,000$ mm $^{-3}$.
2. The incidence of preterm delivery, defined as delivery at <37 weeks' EGA.
3. The incidence of:
 - a. Maternal death
 - b. Perinatal death
4. Number of sickle cell crises
5. Need for blood transfusion – identified based on whether the participant received a blood transfusion or not
6. Incidence of complications such as:
 - a. Urinary tract infection (UTI),
 - b. Lower Respiratory Tract Infection,
 - c. Acute chest syndrome,
 - d. retained placenta,
 - e. placental abruption; and
7. Incidence of potential adverse effects such as:
 - a. vaginal bleeding,
 - b. epigastric pain, and
 - c. heartburn

Analysis will be by intention to treat.

3 Study Methods

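### Among the forms supplied, the delivery e-CRF has no structured item for transfusion, placental abruption, retained placenta or adverse events, so these endpoints risk under-ascertainment

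*Protocol*

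**What the plan says.** **Endpoints.** Protocol 3.9 names among its secondary outcomes "Pregnancy complications: Pre-eclampsia, Preterm delivery, retained placenta, placental abruption", and also the number of blood transfusions. SAP 2.2 repeats abruption and retained placenta and makes transfusion binary: "Need for blood transfusion – identified based on whether the participant received a blood transfusion or not". It also lists vaginal bleeding, epigastric pain and heartburn as potential adverse effects.

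**Tasks at completion.** Protocol 5.5 defines completion as pregnancy loss or delivery. At that visit staff must "Evaluate compliance & ADE" and fill in the delivery e-CRF, the end-of-study e-CRF and other relevant source documents. Protocol 8.3 requires every adverse event to be on the e-CRF with severity, relationship, duration and seriousness.

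**Forms.** The follow-up e-CRF (Appendix 07) asks "Have you had blood transfusion since last visit", with date and units, and has an adverse-event block opening with "Is there an Adverse Event (AE". On the delivery e-CRF (Appendix 08), maternal complications fall under "MATERNAL CONDITION AT MISCARRIAGE / DELIVERY" and consist of six named conditions plus Others with free text. The form also records "Estimated Blood Loss" in three bands, and haemoglobin.

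**The concern.** Transfusion during labour or the postpartum stay, retained placenta, and often abruption arise at or around delivery. That is the one contact for which the supplied form has no structured question about them. The transfusion question looks back to the previous visit, and among the supplied forms it is not repeated once the pregnancy ends. The adverse-event block likewise stops at the last follow-up form, although Protocol 5.5 asks for adverse events to be evaluated at completion.

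At stake are named secondary endpoints and part of the safety comparison. A blank free-text box can mean that the event did not happen or that nobody asked. An analyst cannot tell which, and sites may differ in how they use the box. If the arms differed mainly in that window, the comparison would be distorted as well as less precise.

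**Working it through.** The plan states no figure on this point, so the check sets the forms against the requirements.

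| Item | Required by | Follow-up form (App. 07) | Delivery form (App. 08) | End-of-study form (App. 09) |
|---|---|---|---|---|
| Blood transfusion | Protocol 3.9; SAP 2.2 | Yes/no, date, units | No item; Others free text | None |
| Placental abruption | Protocol 3.9; SAP 2.2 | No item; free text only | No item; Others free text | None |
| Retained placenta | Protocol 3.9; SAP 2.2 | No item; free text only | No item; Others free text | None |
| Adverse events | Protocol 5.5, 8.3 | Structured block | No block | Outcome of a serious event only |

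**Remaining routes for an event at delivery:**
1. Others with free text on the delivery form.
2. The SAE report form (Appendix 11), for events that qualify as serious. It has no item for any of the three endpoints.
3. A visit e-CRF completed for an unscheduled contact (Protocol 5.4), which carries both the transfusion question and the adverse-event block.
4. The Postpartum Visit CRF in SAP 6.1. It is not among the supplied forms, and no appendix cited in the protocol body is a postpartum form. SAP Table 1 lists only maternal and infant physical examinations for that contact.

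**Reporting.** SAP Table shell 3 has a row for transfusion but none for abruption or retained placenta, so incomplete capture of those two could go unnoticed.

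**What under-capture does.** Let *c* be the share of events captured, with no false positives.

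(i) If the same share of *all* events is captured in both arms, recorded risks are *c*·p0 and *c*·p1. The ratio (*c*·p1)/(*c*·p0) = p1/p0 is unchanged, but power falls. Illustration for a binary secondary endpoint, all rates assumed: n = 198 per arm (the evaluable number in the sample-size section), two-sided 5%, p1 = p0/2, and

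power = Φ{(|p0 − p1|·√n − 1.96·√[2p̄(1 − p̄)]) / √[p0(1 − p0) + p1(1 − p1)]},

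with recorded risks put in for p0 and p1, and p̄ their mean. For p0 = 0.20, p1 = 0.10: (0.10 × 14.07 − 1.96 × 0.505)/0.50 = 0.83, so power is 80%. For *c* = 0.5 the recorded risks are 0.10 and 0.05: (0.05 × 14.07 − 1.96 × 0.372)/0.371 = −0.07, so power is 47%.

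| Assumed control risk | c = 100% | 90% | 75% | 50% |
|---|---|---|---|---|
| 10% | 47% | 43% | 37% | 26% |
| 20% | 80% | 75% | 66% | 47% |
| 30% | 95% | 92% | 85% | 66% |

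This shows the mechanism for a secondary endpoint. It does not assess the trial's primary power statement.

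(ii) If under-capture affects only the delivery window, write A for the risk of an event recorded antenatally and D for the risk of an event only at delivery. The recorded ratio is (A1 + *c*·D1)/(A0 + *c*·D0). With A1 = A0 and D1 ≠ D0, it moves towards 1 as *c* falls. Here the loss is bias, not only imprecision.

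**The case against.** The strongest reply is that unstructured is not absent. The Others box can hold abruption, retained placenta or a transfusion. Serious bleeding has the SAE form, an unscheduled-visit form carries the missing questions, and the SAP names a Postpartum Visit CRF. The form printouts are stamped June 2020, whereas the protocol is Version 4 of May 2024, so the current forms may differ. All of this stands. It limits the point to the forms supplied and to a risk rather than a certain loss. It does not close the gap: only an unscheduled visit or an unseen form would ask the question in structured form, and neither is shown to be part of the completion visit.

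Several stronger readings are tempting but lack support:

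- **That a woman transfused only at delivery will be coded as not transfused.** SAP 2.2 defines the endpoint by receipt of a transfusion. No text names the source form or says how a blank is handled.
- **That a real excess on aspirin would be recorded as no difference.** This needs assumed event rates, an excess confined to delivery, and no capture by any route. Protocol 3.4 also stops study drug at 36 weeks or delivery, whichever is earlier, so women delivering later would be off drug. The documents do not establish that harm should concentrate at delivery.
- **That vaginal bleeding and heartburn will not be sought.** The symptom list in Protocol 8.1, ending "abnormal gait, tremor, clonus or dyskinesia, will be sought by the investigator (or designee) at each study visit", names epigastric pain but not these two. It is introduced as examples, however, and volunteered events are also accepted. SAP 8.1 names both symptoms.
- **That the SAP errs in not analysing blood loss.** Blood loss is not an endpoint in Protocol 3.9 or SAP 2.2, so tabulating it would be a preference.

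**Conclusion.** The point holds as an ascertainment weakness in the supplied forms. Delivery-time transfusion and non-serious adverse events have no structured field on the forms named for completion. Abruption and retained placenta have none on any supplied form. Protocol 5.5 and 8.3 and the endpoint lists call for this information.

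The size cannot be computed, because the documents give no event rates for these endpoints and no capture share. Equal under-capture of all events in both arms would leave the risk ratio intact and cost power. Missing a window in which the arms differ would bias the comparison. The documents do not show which applies. The conclusion assumes that the printed forms are those in use and that the Postpartum Visit CRF does not already ask these questions. If it does, the gap closes to the extent that the form is completed.

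**What to change.** **Delivery e-CRF.** Add:
- (a) a yes/no question on transfusion since the last visit that expressly covers labour, delivery and the postpartum stay, with date and units;
- (b) yes/no items for placental abruption and retained placenta;
- (c) the adverse-event block already on the follow-up form.

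If the current Postpartum Visit CRF already has these items, supply it and state which form is the source for each endpoint.

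**SAP.** Add rows for abruption and retained placenta to Table shell 3.

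**Optional.** Name vaginal bleeding and heartburn in the Protocol 8.1 symptom prompt.

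**Cost.** A small REDCap edit and two table rows. For women already delivered, the items can be back-filled from case notes by staff blind to allocation, where feasible. With 15 sites, that note review could be the larger part of the work if recruitment is well advanced.

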APPENDIX 09 – e-End of study

Confidential

PIP-SICKLE

Page 1

End of Study

Record ID

Please enter the date this form is completed

End of Study Category

Normal

Withdraw

Death

LTFU

Date of death

Cause of Death

Gestational Age At Death

(weeks)

(days)

Outcome of Severe Adverse Event (SAE)

Never had SAE

SAE Resolved

Recovered with minor sequelae

Recovered with major sequelae

Ongoing treatment

Condition worsening

Death

Unknown

APPENDIX 09 – DRUG ACCOUNTABILITY FORM

PIPSICKLE TRIAL

INVESTIGATIONAL DRUG ACCOUNTABILITY RECORD

Study site Name:										
Site Code:						Total Quantity Received/Date: (including Replacement kits)				
Site Investigator:						Test Drug:				
Study Title:						Batch No. :				
						Mfg Date :				
						Expiry Date :				
Subject initials	Subject ID	Drug Kit Number/ RC	Visit type (E or F)	Date dispense d	Dispensed By/Initials	Date Returne d	Amount of Drug present	Site personnel Signature	CRA/Monitor Signature	

RC- Randomisation code E= Enrollment F- Follow-up

